6.4 Appendix 4: Qualitative interview guide

After explaining the purpose of the walking interview and informed consent open ended questions will be asked to explore their lived experiences of using the off-loading device and facilitators and barriers to use of such devices.

The walking route will be no more than in and around the home or other place where participant performs daily routine activities.

- What is your experience on using this off-loading device?
- What made you to wear this device continuously (at least while walking)
 - Explain all reasons that made you to wear this device.
- What are the difficulties that you faced while using this device?
 - Explain the individual difficulties you faced
- How easy or difficult for you to do your essential routine activities with device on
- Would you suggest any modifications to improve the effectiveness of the device to heal ulcer at the same time improve adherence to it

7 References

2. Meima A, van Veen NH, Richardus JH. Future prevalence of WHO grade 2 impairment in relation to incidence trends in leprosy: an exploration. Trop Med Int Health. 2008;13(2):241-6.

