1.9 Qualitative interview

User experience on removable walker boot will be explored through semi-structured walking interviews. An estimate of fifteen patients in each site, sampled purposively, will be asked about their experiences of using the device. In the interviews we will seek to elicit reasons for adherence and non-adherence to removable walker.

2 Background

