2.3 Current use of off-loading methods to heal plantar ulcers in LMICs

Studies in high income countries show adherence with removable off-loading devices ranging from 28% to 60% (≥80% of daily steps/time) .(22) The situation may be very different in low and middle income countries (LMIC).

We conducted a literature review with the aim of understanding the effectiveness of total contact casts compared to removable off-loading devices for plantar ulcers in patients with diabetes mellitus or leprosy in LMIC. We sought to understand the predictors of adherence to using off-loading devices to heal plantar ulcers to diabetes mellitus or leprosy and any difference in healing rates. Our database search yielded 250 potentially relevant abstracts. These abstracts were reviewed by two researchers. We included 8 studies in the review, 5 randomized control trials; and 3 case series. The majority of the studies identified focused on people with diabetes (n=6)(23, 24, 25, 26, 27, 28) and only one study focused on people affected by leprosy (29) . The final study, a case series,1 included a mixed population of people affected by leprosy, diabetes and meningomyelocele.(30) The majority of the studies (n=5)

used total contact cast (25, 27, 30, 31, 32) as off-loading method and found it to be superior to other techniques (modified ankle foot orthosis (26), removable ankle high cast, (33) and standard dressing (25, 32). Adherence to cast use has been reported to be a major concern but none of the studies measured adherence objectively.(25, 26, 27, 29, 30) None of the studies used removable off-loading devices of the type we propose to test in this study. As a result of difficulties in procurement and support, the great majority of people in LMICs with neuropathic ulcers receive none of the above devices and are provided with footwear with a soft insole of Micro-cellular rubber.

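### The interview guide's one question on wearing the boot assumes continuous wear, and no item asks directly when or why it was left off, although reasons for non-adherence are a stated aim.

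*Protocol*

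**What the plan says.** Section 1.9 of the protocol sets the aim of the interviews: "In the interviews we will seek to elicit reasons for adherence and non-adherence to removable walker". Section 4.8 describes semi-structured walking interviews with intervention-arm participants, estimated at fifteen per site and arranged 2 to 4 weeks after the boot is received. Participants are to explain how using or not using it affects their routines and mobility, and to describe the challenges they meet.

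Appendix 4 (Section 6.4) is the interview guide. Its introduction gives the scope as lived experience and "facilitators and barriers to use of such devices". Five questions follow. The one on wearing is "What made you to wear this device continuously (at least while walking", and the probe beneath it is "Explain all reasons that made you to wear this device".

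Sections 4.5 and 4.5.1 supply the context. Participants are taught the importance of adherence, and those given the boot are taught to open it only for dressing changes.

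**The concern.** The aim has two sides, adherence and non-adherence, but the guide puts a direct question on only one. That question also presupposes its answer, since it asks what made the participant wear the boot continuously and not whether they did. Someone who left the boot off has to reject the premise before giving the reason. They must do so in front of a researcher from the study that told them to keep it on, at a point inside the 8-week follow-up unless the ulcer has already healed. This is a recognised setting for socially desirable answers.

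At stake is how well the interviews deliver reasons for not wearing the boot. Adherence is the first primary feasibility objective, and Section 2.2 treats understanding what drives adherence as essential to improving off-loading treatment. The pedometers can show how much the boot was worn but not why it was left off.

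**Working it through.** No sample size, power or error rate is involved, so the check compares the stated aim with the guide item by item.

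**What the interviews are meant to cover**
- Section 1.9: reasons for adherence and for non-adherence.
- Section 4.8: effects of use and of non-use, challenges, and how participants deal with them.
- Appendix 4, introduction: facilitators and barriers.

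**What each of the five questions asks**
1. Experience of using the device. Open and neutral. Non-wear may come up but is not asked about.
2. "What made you to wear this device continuously (at least while walking", with the probe "Explain all reasons that made you to wear this device". This is the one question on wearing. The main wording assumes continuous wear, softened to the time spent walking. The probe asks for reasons for wearing and has no counterpart on not wearing.
3. "What are the difficulties that you faced while using this device", with a probe on each difficulty. This is an indirect route to reasons for non-wear, framed around periods of use.
4. "How easy or difficult for you to do your essential routine activities with device on". Also indirect, and framed around the boot being on.
5. "Would you suggest any modifications to improve the effectiveness of the device to heal ulcer at the same time improve adherence to it". This accepts that adherence could be better, but it asks for suggested changes and not for the participant's own reasons for leaving the boot off.

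**Tally**
- Questions whose wording assumes continuous wear: 1 of 5 (question 2, with its probe).
- Questions asking directly whether, when or why the boot was not worn: 0 of 5.
- Questions that approach barriers indirectly: 3 of 5 (questions 3, 4 and 5), plus whatever the open question 1 brings up.

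**Comparison.** The adherence half of the Section 1.9 aim has a direct question and a dedicated probe. The non-adherence half has neither. Section 4.8 includes non-use in the interview, and the guide does not carry that into a question.

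**The case against.** The strongest reply is that the interviews cover barriers well enough without a direct question. The guide names barriers in its scope. Two questions concern difficulty and a third asks how adherence could be improved. The questions are open-ended, the format is semi-structured, the researcher may spend up to half a day with each participant, and Section 4.8 tells interviewers to cover non-use. All of this stands, and it rules out several stronger readings that a reader might infer:

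- *That the interviews as a whole presuppose adherence.* Only one question and its probe do.
- *That a non-wearer has no place to explain.* The experience, difficulties, routine-activities and modifications questions all give an opening, though an indirect one.
- *That the conclusions will be biased towards facilitators.* The balance of items does not show this, since more questions concern difficulty or improvement than reasons for wearing.
- *That the interviews are the only source of reasons.* Appendix 3 has a comment line on each of the eight QUEST 2.0 items and a free-text field for device-related adverse events. Neither asks about non-wear, but both can record likely barriers.
- *That the number of interviewees affected can be calculated.* Section 2.3 cites "adherence with removable off-loading devices ranging from 28% to 60" per cent, and it is tempting to apply the complement to the interview sample. Those figures come from high-income countries, and the same section warns that low- and middle-income settings may differ greatly. They also define adherence as at least 80% of daily steps or time, which is not the premise of the question. A person below that threshold can still say why they wear the boot, and a person above it may not wear it continuously.

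The reply does not remove the mismatch itself. A stated aim is left to indirect questions and to each interviewer's follow-up, across two countries and in translation, while the one direct question on wearing leads the participant.

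**Conclusion.** The point holds in limited form. The guide has one leading question and probe on continuous wear and no direct counterpart on non-wear, so the non-adherence half of the Section 1.9 aim is covered only indirectly. The documents establish the wording, the missing counterpart and the instruction to keep the boot on. That the wording will draw socially desirable answers is a judgement about interviewing. It is reasonable here, but the documents do not measure it and no size can be put on it.

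This is a minor defect in the qualitative instrument. It does not affect the pedometer measure of adherence, the satisfaction score, the healing comparison or the sample size. It is still worth correcting, because it bears on a stated output of the feasibility study and the correction is practically free.

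**What to change.** In Appendix 4, replace the question on continuous wear and its probe with a neutral pair:

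- *When do you wear the device, and when do you not?*
- *What makes you put it on, and what makes you take it off or leave it off?*

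Give equal probes for wearing and not wearing. The other four questions can stay as they are. The guide would then match Sections 1.9 and 4.8.

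The cost is rewording one question and its probe and carrying the change into the translated versions. It adds no visits or staff and negligible interview time, and it leaves the quantitative analysis unchanged.
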